1.2.2. Definition of Study Drugs

Study drug comprises the following (placebo and 3 doses of TD-1473):

- TD-1473 20 mg (2 x 10 mg tablets) once daily: Taken orally for up to 16 (including Extended Induction when applicable) weeks in the morning. With the exception of clinic visit days, subjects will be instructed to take two tablets once daily at approximately the same time each morning.
- TD-1473 80 mg (2 x 40 mg tablets) once daily: Taken orally for up to 16 (including Extended Induction when applicable) weeks in the morning. With the exception of clinic visit days, subjects will be instructed to take two tablets once daily at approximately the same time each morning.
- TD-1473 200 mg (2 x 100 mg tablets) once daily: Taken orally for up to 16 (including Extended Induction when applicable) weeks in the morning. With the exception of clinic visit days, subjects will be instructed to take two tablets once daily at approximately the same time each morning.
- Placebo once daily: Taken orally for up to 8 (Induction period only) weeks in the morning. With the exception of clinic visit days, subjects will be instructed to take two tablets once daily at approximately the same time each morning. Note: Subjects who do not respond on placebo during Induction Period will be switched to TD-1473 80 mg (2 x 40 mg tablets) once daily for the Extended Induction period.

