3.7.1. Extent of Exposure

Study drug exposure will be summarized using the 8-point descriptive summary presenting number of doses and duration of treatment separately for the induction phase and complete study separately.

Duration of treatment will be displayed in weeks and calculated for the induction period as:

$$\frac{(last\ induction\ phase\ dose\ date - first\ dose\ date + 1)}{7}$$

*Last induction phase dose date is the Week 8 visit dose administration date for those that reach the Week 8 visit or equal to date of last study drug return for those who discontinue prior to Week 8 visit.

Duration of treatment for the entire study period will also be displayed in weeks and calculated as:

$$\frac{(last\ study\ drug\ return\ date - first\ dose\ date + 1)}{7}$$

Calculated values will be rounded to 1 significant digit in the analysis datasets and summary statistics will be presented to the follow significant digits:

- Mean, median, Q1, Q3: 1 significant digit
- Standard deviation: 2 significant digits
- Minimum, maximum: 1 significant digit

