5.2.1.6. Time Since Ulcerative Colitis Diagnosis

Time since UC diagnosis (years) as of the first dose date is calculated as (first dose date - diagnosis date)/365.25. It is left unrounded for calculation of summary statistics but rounded to 1 decimal place for display.

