1.2. Study Design

This single protocol includes three studies: a Phase 2b dose-finding Induction Study, a Phase 3 dose-confirming Induction Study, and a Phase 3 randomized-withdrawal Maintenance Study (Figure 1).

Figure 1: Protocol Schema

* Estimated number of subjects for the re-randomized maintenance population

Each of the three studies will utilize a multi-center, randomized, double-blind, placebo-controlled, parallel-group design to evaluate various doses of TD-1473 compared to placebo in subjects with moderately-to-severely active ulcerative colitis (UC).

The Induction Studies will target subjects with moderately-to-severely active UC who demonstrate an inadequate response or failure to tolerate conventional or biologic therapy.

The Maintenance Study will be a randomized withdrawal study targeting subjects with moderately-to severely-active UC who demonstrate a clinical response to induction treatment with TD-1473.

Maintenance Study

In summary, subjects who demonstrate clinical response to a total of 8 weeks of TD-1473 induction therapy, either at Week 8 or Week 16, will be re-randomized. Those who demonstrate response to placebo at Week 8 or those who demonstrate response to a total of 16 weeks of TD-1473 treatment at Week 16 will enter the Maintenance Study on the same study drug treatment as during Induction for the purpose of maintaining blinding. The Maintenance Study consists of treatment for 44 weeks. During the Maintenance Study, subjects must taper their corticosteroid dose using the regimen outlined in Section 6.5.3 if they entered the study on corticosteroids.

The randomization will be stratified by clinical remission status at mWeek 0 using adapted Mayo score component definition, and corticosteroid use at enrollment into the Phase 3 Maintenance Study. In addition, randomization will also be stratified by subjects who reach clinical response after receiving 8 weeks of TD-1473 versus subjects who reach clinical response after receiving placebo during the first 8 weeks and then TD-1473 80 mg during extended induction.

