3.7.1. Extent of Exposure

Study drug exposure will be summarized using the 8-point descriptive summary presenting number of doses and duration of treatment separately for the induction phase and complete study separately.

Duration of treatment for the study will be displayed in weeks and calculated as:

$$\frac{(\text{last study drug return date} - \text{first dose date} + 1)}{7}$$

Calculated values will be rounded to 1 significant digit in the analysis datasets and summary statistics will be presented to the follow significant digits:

- Mean, median, Q1, Q3: 1 significant digit
- Standard deviation: 2 significant digits
- Minimum, maximum: 1 significant digit

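### Section 3.7.1 of both SAPs rounds treatment duration in weeks to 1 significant digit, so 12, 16 and 44 weeks become 10, 20 and 40; probably a slip for 1 decimal place

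*SAP*

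**What the plan says.** Both SAPs derive duration of treatment as (last date − first dose date + 1)/7. The Phase 2b SAP does this for the induction period and again for the whole study: "Duration of treatment for the entire study period will also be displayed in weeks and calculated as". The Maintenance SAP has one version: "Duration of treatment for the study will be displayed in weeks and calculated as". For the whole-study and Maintenance figures, the last date is the last study drug return date.

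Both sections then give the same precision rule: "Calculated values will be rounded to 1 significant digit in the analysis datasets". They set the display of the summaries in the same units: "Mean, median, Q1, Q3: 1 significant digit", with minimum and maximum also at 1 and "Standard deviation: 2 significant digits". Neither SAP defines a significant digit in any special way.

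Planned exposure for the active doses in Phase 2b is "Taken orally for up to 16 (including Extended Induction when applicable) weeks in the morning" (Phase 2b SAP, Section 1.2.2). For Maintenance, "The Maintenance Study consists of treatment for 44 weeks" (Maintenance SAP, Section 1.2).

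The Phase 2b SAP treats another duration differently. For time since diagnosis (Section 5.2.1.6), "It is left unrounded for calculation of summary statistics but rounded to 1 decimal place for display".

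**The concern.** One significant digit is a very coarse scale for values between 10 and 50: the only values available are 10, 20, 30, 40 and 50. Planned exposure in Extended Induction and Maintenance lies in that range. The rule acts on each subject's value before any statistic is computed, and the statistics are then rounded again. A display format of 1 decimal place would not bring back what was lost in the dataset variable; duration would have to be re-derived from the dates.

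The precision pattern is also odd as written. An SD with 2 significant digits beside a mean with 1 could produce, for example, a mean of 12.3 printed as 10 next to an SD of 4.2.

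What is at stake is the description of how long subjects were treated. Exposure is part of the planned safety analysis in both SAPs, and safety over up to 44 further weeks is a primary objective of the Maintenance Study.

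**Working it through.** The documents print no duration result, so there is no figure to reproduce first. The check applies the stated rule to plausible durations.

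**Inputs.** The duration formula and rounding rule come from Section 3.7.1 of both SAPs. The planned 16 and 44 weeks come from Phase 2b SAP Section 1.2.2 and Maintenance SAP Section 1.2. The visit windows come from protocol Table 1: Week 8a at −3 to +5 days, and the next visit 1 to 7 days after it.

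**Formula.** Weeks w = days/7. With k = floor(log10 w), the value to 1 significant digit is round(w/10^k) × 10^k, halves rounded up.

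| Days | Exact weeks | 1 significant digit | Error | 1 decimal place |
|---|---|---|---|---|
| 56 | 8.0 | 8 | 0% | 8.0 |
| 60 | 8.571 | 9 | +5.0% | 8.6 |
| 84 | 12.0 | 10 | −16.7% | 12.0 |
| 104 | 14.857 | 10 | −32.7% | 14.9 |
| 105 | 15.0 | 20 | +33.3% | 15.0 |
| 112 | 16.0 | 20 | +25.0% | 16.0 |
| 308 | 44.0 | 40 | −9.1% | 44.0 |
| 315 | 45.0 | 50 | +11.1% | 45.0 |

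**Ranges that collapse to one value.**
- 67 to 104 days (9.57 to 14.86 weeks) become 10.
- 105 to 174 days (15.0 to 24.86 weeks) become 20.
- 175 to 244 days (25.0 to 34.86 weeks) become 30.
- 245 to 314 days (35.0 to 44.86 weeks) become 40.
- From 315 days (45.0 weeks) the value is 50.

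One extra day, from 104 to 105 or from 174 to 175, adds ten weeks to the recorded exposure. The exact ties at 175 and 315 days depend on rounding halves up; one day later (176/7 = 25.14, 316/7 = 45.14) the result is 30 and 50 under any rounding convention.

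**Induction period.** Week 8a falls on day 56 − 3 = 53 to day 56 + 5 = 61, and the next visit can be as late as day 61 + 7 = 68. Across 53 to 68 days the largest error is at 53 days: 7.571 becomes 8, or +5.7%. Other points are 59 days (8.43 to 8, −5.1%) and 68 days (9.71 to 10, +2.9%). Between 1 and 10 weeks the rule rounds to whole weeks, so the error is at most 3/7 = 0.43 week, including for subjects who stop early.

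**What uses this variable.** Compliance (Section 3.7.1.1 in both SAPs) is computed from dates and tablet counts. Adverse event tables (Section 3.7.2 in both) give numbers and percentages of subjects, with no exposure-adjusted rates. No efficacy analysis includes duration of treatment.

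**The case against.** The best reply is that nobody would program this literally. One digit for the mean, two for the SD and one for the range is the usual decimal-place pattern, and Section 5.2.1.6 of the Phase 2b SAP uses decimal places for a comparable quantity. A programmer who saw 16 weeks turn into 20 would ask. This stands as an account of intent and keeps the point minor. It does not make the text right: the term has a standard meaning, it is used throughout both sections, and nothing elsewhere corrects it.

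Four stronger readings are tempting, and the documents do not support them.

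- *The rule biases the comparison between arms.* The protocol (Section 8.8) makes the first 8 weeks the primary safety period, and induction duration is summarized separately. All four arms have about 8 weeks planned there, and the shift within visit windows is small. The large shifts arise in whole-study summaries that include Extended Induction, which is not placebo-controlled. Subjects who move from placebo to 80 mg are shown as a separate group (Phase 2b SAP, Section 3.7).
- *It distorts adverse event rates.* Duration is not a denominator in the planned adverse event tables.
- *It understates exposure for every Maintenance completer, and nearly all Maintenance durations exceed 10 weeks.* Duration runs to the drug return date, so 315 days or more is overstated as 50. The study was stopped early (Maintenance SAP, Section 1), and no exposure distribution is given.
- *The loss is permanent.* The source dates are collected, and in Phase 2b the first and last dose dates are listed (Section 3.2.1), so duration can be re-derived.

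**Conclusion.** The point holds as a wording error in a stated analysis rule, present in both SAPs. Taken literally, it records 12.0 weeks as 10, 16.0 as 20 and 44.0 as 40. It would distort the descriptive whole-study exposure summary in Phase 2b and the exposure summary in Maintenance. Induction durations change by about 6% or less for subjects seen within the protocol's windows, and efficacy tests, compliance and adverse event percentages are untouched.

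This rests on two assumptions: significant digit carries its ordinary meaning, and halves round up. Whether the literal rule was ever programmed cannot be told from the documents. It is most likely a slip for 1 decimal place, and the severity is minor.

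**What to change.** In Section 3.7.1 of both SAPs:

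- Delete the clause that rounds values in the analysis datasets, and state that duration is kept unrounded for calculation, as Section 5.2.1.6 of the Phase 2b SAP already does for time since diagnosis.
- Present mean, median, Q1, Q3, minimum and maximum to 1 decimal place, and SD to 2 decimal places.

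Simply replacing significant digit with decimal place throughout would leave values rounded to 0.1 week in the datasets. That also removes the distortion (error at most 0.05 week), but it would not match Section 5.2.1.6, so deleting the clause is cleaner.

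The cost is one wording change per SAP, with no new data or analysis. If exposure tables have already been produced, check that the duration variable was not rounded to 1 significant digit.

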3.7.1.1. Treatment Compliance

Study drug compliance will be calculated as:

$$\frac{100 \times 0.5 \times (number\ of\ capsules\ dispensed - number\ of\ capsules\ returned)}{(date\ of\ last\ dose - date\ of\ first\ dose + 1)}$$

Study drug compliance over the interval from first to last dose in the induction period will be summarized as a continuous variable and by rounding to the nearest 0.1% and showing counts and percentages for the following disjoint categories:

Label
≥ 120%;
110% to 120%;
90% to 110%;
80% to 90%;
< 80%;

Study drug administration information (date/time and study day) will be provided in a data listing. Study drug accountability information and study drug exposure and compliance will also be provided in data listings.

Study drug discontinuations and reasons for study drug discontinuation will be listed.

3.7.2. Adverse Events

Adverse events (AEs) will be coded to the preferred terms (PT) of the Medical Dictionary for Regulatory Activities (MedDRA®). Summaries for induction period and for the complete study period will be presented separately and by system organ class (SOC), preferred term, and severity and/or relatedness, the number and percentage of subjects for whom events were reported.

Adverse events (AEs) are recorded from signing of the informed consent form through the final follow-up assessment. Adverse events observed prior to first dose are non-treatment emergent.

Treatment emergent adverse events are defined as follows for induction period and overall:

- TEAEs are AEs with onset on or after the first initiation of study drug up to the date of last dose of study drug + 28 days.

Only treatment-emergent AEs will be summarized in the tables.

An AE will be considered a treatment-emergent serious AE (TESAE) if it is a TEAE that additionally meets any SAE criteria.

If more than 1 AE is coded to the same preferred term for the same subject, the subject will be counted only once for that preferred term using the most severe and most related occurrence for the summarizations by severity and by relationship to study drug.

Summary tables will also be provided for Induction period and overall for subjects with:

- TESAEs by SOC and PT
- TEAEs leading to discontinuation of study drug by SOC and PT
- Drug related TEAEs by SOC and PT
- TEAEs by severity and by SOC and PT
- TEAEs resulting in death by PT

Listings of all AEs, SAEs, and AEs leading to discontinuation by subject will be presented.

An overall summary of adverse events will also be presented and will include the following summary lines: Any AE, Moderate or Severe AEs, AEs Related to Study Drug, Moderate or Severe AEs Related to Study Drug, Serious AEs, Serious AEs Related to Study Drug, AEs Leading to Premature Study Drug Discontinuation, AEs Leading to Temporary Interruption of Study Drug, and Deaths During Study.

3.7.2.1. Adverse Events of Special Interest

An AE of special interest (AESI) is one of scientific and medical interest specific to understanding the investigational product and may require close monitoring and rapid communication by the investigator to the sponsor. The following are the AESI's defined for the study:

- Suspected or Confirmed Intestinal Perforation
- Complicated Herpes Zoster (multi-dermatomal, disseminated, or with ophthalmic or CNS involvement)
- Malignancy excluding non-melanoma skin cancer
- Non-melanoma skin cancer
- Serious Infection (e.g., that requires hospitalization or intravenous antibiotics)
- Opportunistic Infections
- Thromboembolic disease (e.g. deep vein thrombosis, pulmonary embolism)

- Clinical Laboratory Abnormalities of Concern
- Cardiovascular Event (e.g. myocardial infarction or cerebrovascular accident)

The incidence of AESI's will be summarized overall and by AESI category and preferred term.

3.7.3. Additional Safety Assessments

3.7.3.1. Clinical Laboratory Parameters

Laboratory data, hematology, serum chemistry and urinalysis, will be summarized in terms of observed values and changes from baseline for induction period and overall. In addition, changes from baseline relative to normal ranges from the central lab (e.g., shifts from normal to abnormal high/low) will be summarized.

Summaries for laboratory parameters of special interest will also be presented, these will include:

- Neutrophils
- Leukoocytes
- Lymphocytes
- Hemoglobin
- Lipids [LDL cholesterol, HDL cholesterol, Cholesterol, and Triglyceride]
- Liver Function Test's [ALT, AST, Bilirubin]
- Creatinine
- Creatinine Kinase

The number and percentage of subjects with clinically abnormal lab values will also be summarized by timepoint for the following criteria:

- absolute neutrophil count of $< 1.0 \times 10^9/L$
- white blood cell count of $< 2.0 \times 10^9/L$
- absolute lymphocyte count of $< 0.5 \times 10^9/L$

A summary of maximum National Cancer Institute Common Terminology Criteria for Adverse Events (NCI-CTCAE) toxicity grade (Appendix 5.8) for postbaseline laboratory values through Week 8 and through Week 16.

Listings will flag laboratory values that are outside of normal range.

A listing of all abnormal lab values will be provided. Listings of subjects with any abnormal postbaseline laboratory values of CTCAE grade ≥ 2 will also be provided.

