(or serious adverse event), as described in Section 7.1.1 (Adverse Event) and Section 7.1.2 (Serious Adverse Event).

Clinical laboratory abnormalities of concern may include, but are not limited to, the following where the investigator must recheck within 2-7 days, except for AST or ALT > 3x ULN where these need to be rechecked within 48-72 hours, as deemed appropriate by the investigator:

- clinically significant reduction in neutrophils or leukocytes or lymphocytes that may place subjects at higher risk for infection such as:
 - moderate or severe neutropenia (e.g., absolute neutrophil count of $< 1.0 \times 10^9/L$)
 - moderate or severe leukopenia (e.g., white blood cell count of $< 2.0 \times 10^9/L$)
 - moderate or severe lymphocytopenia (e.g., absolute lymphocyte count of $< 0.5 \times 10^9/L$)
- abnormal hepatic panel (AST or ALT > 3x ULN)
- an excessive decrease in creatinine clearance (e.g., a reduction by $\geq 50\%$ from baseline (baseline for this purpose is defined as creatinine clearance calculated for Day 1, predose activities))

Depending on the subject's baseline and individual scenario, the investigator should report as an AESI and stop study drug treatment if any of the below is seen:

- moderate or severe neutropenia (e.g., absolute neutrophil count of $< 1.0 \times 10^9/L$) on two sequential laboratory reports
- moderate or severe leukopenia (e.g., white blood cell count of $< 2.0 \times 10^9/L$) on two sequential laboratory reports
- moderate or severe lymphocytopenia (e.g., absolute lymphocyte count of $< 0.5 \times 10^9/L$) on two sequential laboratory reports
- a reduction by $\geq 50\%$ from baseline in creatinine clearance on two sequential laboratory reports
- Abnormal AST or ALT > 3x ULN on two sequential laboratory reports with bilirubin > 2x ULN on at least one of the two laboratory reports or international normalized ratio (INR) > 1.5 on at least one of the two reports (INR will be checked locally)
- AST or ALT > 5x ULN on two sequential laboratory reports at least 2 weeks apart
- AST or ALT > 3x ULN associated with signs or symptoms suggestive of acute liver injury (e.g., the appearance of fatigue, nausea, vomiting, right upper quadrant pain or tenderness, fever, rash, and/or eosinophilia [$> 5\%$])
- AST or ALT > 8x ULN on one laboratory report

Note: See [Appendix 10](#) for an algorithm of evaluating and managing subjects with ALT or AST > 3x ULN.

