8.8.4. Laboratory Data

Laboratory values, changes from baseline, values relative to normal ranges, and values and changes meeting specified criteria of special interest (including those given in Section 6.2) will be summarized.

Reference ranges provided by the laboratory for each test will be used to evaluate the clinical significance of laboratory test results. Values falling outside the relevant reference range will be flagged, as appropriate, in the data listings. A separate listing or listings will be provided for abnormalities in clinical laboratory test results.

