5.8. CTCAE Grading

Grading Criteria for Clinical Laboratory Tests [CTCAE Version 5.0]					
Hematology Tests		Criteria			
Test	Direction	1	2	3	4
Hemoglobin (g/L)	Decrease	≥ 100 - <LLN	≥ 80 - <100.0	≥ 65 - <80	<65
Leukocytes (WBC) ($10^9/L$)	Decrease	≥ 3.0 - <LLN	≥ 2.0 - <3.0	≥ 1.0 - <2.0	<1.0
Lymphocytes ($10^9/L$)	Decrease	≥ 0.8 - <LLN	≥ 0.5 - <0.8	≥ 0.2 - <0.5	<0.2
Neutrophils ($10^9/L$)	Decrease	≥ 1.5 - <LLN	≥ 1.0 - <1.5	≥ 0.5 - <1.0	<0.5
Platelets ($10^9/L$)	Decrease	≥ 75.0 - <LLN	≥ 50.0 - <75.0	≥ 25.0 - <50.0	<25.0
Chemistry Tests		Criteria			
Test	Direction	1	2	3	4
ALT	Increase	>ULN - ≤ 3.0 Xuan if baseline was normal; 1.5 - 3.0 x baseline if baseline was abnormal	>3.0 xULN - ≤ 5.0 xULN if baseline was normal; >3.0 - 5.0 x baseline if baseline was abnormal	>5.0 xULN - ≤ 20.0 xULN if baseline was normal; >5.0 - 20.0 x baseline if baseline was abnormal	>20.0 xULN if baseline was normal; >20.0 x baseline if baseline was abnormal
Albumin (g/L)	Decrease	≥ 30 - <LLN	≥ 20 - <30	<20	
Alkaline Phosphatase	Increase	>ULN - ≤ 2.5 xULN if baseline was normal; 2.0 - 2.5 x baseline if baseline was abnormal	>2.5 xULN - ≤ 5.0 xULN if baseline was normal; >2.5 - 5.0 x baseline if baseline was abnormal	>5.0 xULN - ≤ 20.0 xULN if baseline was normal; >5.0 - 20.0 x baseline if baseline was abnormal	>20.0 xULN if baseline was normal; >20.0 x baseline if baseline was abnormal
AST	Increase	>ULN - ≤ 3.0 xULN if baseline was normal; 1.5 - 3.0 x baseline if baseline was abnormal	>3.0 xULN - ≤ 5.0 xULN if baseline was normal; >3.0 - 5.0 x baseline if baseline was abnormal	>5.0 xULN - ≤ 20.0 xULN if baseline was normal; >5.0 - 20.0 x baseline if baseline was abnormal	>20.0 xULN if baseline was normal; >20.0 x baseline if baseline was abnormal
Bilirubin	Increase	>ULN - ≤ 1.5 xULN if baseline was normal; > 1.0 - 1.5 x baseline if baseline was abnormal	>1.5 xULN - ≤ 3.0 xULN if baseline was normal; >1.5 - 3.0 x baseline if baseline was abnormal	>3.0 xULN - ≤ 10.0 xULN if baseline was normal; >3.0 - 10.0 x baseline if baseline was abnormal	>10.0 xULN if baseline was normal; >10.0 x baseline if baseline was abnormal
Calcium (mmol/L)	Increase	>ULN - ≤ 2.9	>2.9 - ≤ 3.1	>3.1 - ≤ 3.4	>3.4

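### The SAP counts only the three blood-count criteria of Protocol 7.2; its hepatic and creatinine-clearance criteria have no threshold-based count, and CTCAE grades do not reproduce them

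*SAP*

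**What the plan says.** Protocol 7.2 has two lists. The first names abnormalities that call for a recheck: low neutrophils, white cells or lymphocytes, an "abnormal hepatic panel (AST or ALT > 3x ULN"), and "an excessive decrease in creatinine clearance" of at least 50% from Day 1. The second names findings to be reported as an AESI with study drug stopped. It includes the blood counts and a halving "from baseline in creatinine clearance on two sequential laboratory reports"; AST or ALT above 3x ULN on two reports with bilirubin above 2x ULN or INR above 1.5; AST or ALT above 5x ULN on two reports at least 2 weeks apart; AST or ALT above 3x ULN with symptoms; and "AST or ALT > 8x ULN on one laboratory report".

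Protocol 8.8.4 says the laboratory summaries will cover "values and changes meeting specified criteria of special interest (including those given in Section 6.2"). Section 6.2 is Total Blood Volume and contains no laboratory criterion. Protocol 8.1 requires changes to the planned summaries to be described in the SAP.

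In Phase 2b SAP 3.7.3.1 the sentence "The number and percentage of subjects with clinically abnormal lab values will also be summarized by timepoint for the following criteria" is followed by three rows, at exactly the 7.2 blood-count cut-offs (1.0, 2.0 and 0.5 x10^9/L). The Maintenance SAP section of the same number has the same three. Appendix 5.1 of the Phase 2b SAP records only the move to estimands. Appendix 5.1 of the Maintenance SAP records only efficacy changes.

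**The concern.** The SAP rows match the blood-count part of 7.2 and omit the hepatic and renal part, with no explanation. Protocol 1.5 names liver function tests and serum creatinine among the effects seen with a systemic JAK inhibitor, and safety is a step in the dose selection of Protocol 8.11. A reader of the report would expect to see, by arm, how many subjects crossed the protocol's own hepatic and renal thresholds according to the laboratory data. As planned, the nearest laboratory-based summary is maximum CTCAE grade. The question is whether those grades carry the same information.

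**Working it through.** The plan gives no figure to reproduce. The check runs the 7.2 thresholds through the grading rules of Phase 2b SAP Appendix 5.8.

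**Inputs**
- Exclusion criterion 20a (Protocol 4.2) is set at AST or ALT of 2x ULN or more at screening, so baselines between 1x and 2x ULN can enter.
- ALT/AST grades, normal baseline: Grade 1 to 3x ULN, Grade 2 to 5x, Grade 3 to 20x. Abnormal baseline: Grade 1 is "1.5 - 3.0 x baseline if baseline was abnormal", Grade 2 runs to 5.0x baseline.
- Bilirubin grades: cuts at 1.5, 3.0 and 10 times ULN (normal baseline) or times baseline (abnormal baseline).
- Creatinine grades: cuts at 1, 1.5, 3 and 6x ULN, with no baseline term.
- Creatinine clearance (SAP 5.2.1.9): (140 - age) x ideal body weight / (72 x creatinine), times 0.85 in women.

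**Step 1. ALT and AST.** With a normal baseline, above 3x ULN is Grade 2 or more and above 5x ULN is Grade 3 or more, so both cuts are recovered. Above 8x ULN is not: it lies inside Grade 3 (5x to 20x). With an abnormal baseline b (in x ULN), the Grade 1 ceiling is 3b and the Grade 2 ceiling is 5b:

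| Baseline (x ULN) | Grade 1 up to | Grade 2 up to |
|---|---|---|
| 1.2 | 3.6x ULN | 6.0x ULN |
| 1.5 | 4.5x ULN | 7.5x ULN |
| 1.9 | 5.7x ULN | 9.5x ULN |

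From 1.9x ULN, a value of 5.5x ULN is 5.5/1.9 = 2.89 times baseline: Grade 1, and outside the listing of Grade 2 or more. A value of 8.1x ULN is 8.1/1.9 = 4.26 times baseline: Grade 2.

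**Step 2. Bilirubin and the joint rule.** With a normal baseline, 2x ULN lies inside Grade 2 (1.5x to 3.0x). With a baseline of 1.5x ULN, 2.1x ULN is 2.1/1.5 = 1.4 times baseline: Grade 1. Grades are assigned test by test, so nothing joins ALT or AST with bilirubin in the same subject.

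**Step 3. Creatinine clearance.** With age and ideal body weight fixed, clearance is proportional to 1/creatinine, so a 50% fall is a doubling of creatinine. From baseline c (in x ULN) the new value is 2c:
- c at or below 0.5: 2c is at most 1, no grade.
- c above 0.5 and up to 0.75: 2c is above 1 and at most 1.5, Grade 1.
- c above 0.75: Grade 2 or more.

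The misses are therefore at low-normal baselines. At raised baselines the grade catches a halving but is not specific to it. From 1.2x ULN a halving gives 2.4x ULN, Grade 2, while a 25% fall gives 1.2/0.75 = 1.6x ULN, also Grade 2.

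**Step 4. Other outputs.** The Phase 2b SAP also summarizes ALT, AST, bilirubin and creatinine as parameters of special interest, but sets no threshold for them. Creatinine clearance is derived in 5.2.1.9, yet no visible summary reports it. The Maintenance SAP has neither the special-interest parameter list nor the listing of Grade 2 or more.

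**The case against.** The strongest case against is that these subjects are captured elsewhere. Protocol 7.2 tells the investigator to report an AESI and stop study drug, and Protocol 6.6.1 repeats the discontinuation. The AESI table (SAP 3.7.2.1) has a category for laboratory abnormalities of concern, SAP 3.7.2 tabulates and lists adverse events leading to discontinuation, and 3.7.3.1 lists every abnormal value whatever its grade. Protocol 8.11 allows the Dose Selection Committee unblinded listings of markedly abnormal laboratory values. All of this stands. A reader might infer that subjects who met a stopping criterion would vanish from the report, or that doses would be chosen without sight of hepatic or renal signals. The documents do not support either inference.

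Two further points also stand. The worked values are single readings, whereas the 5x ULN and clearance stopping rules each need two reports, so one value of 5.5x ULN does not meet a stopping rule. And 7.2 is written to guide the care of individual subjects, in open-ended terms; that 8.8.4 means 7.2 is an inference, though 6.2 cannot be meant.

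What the objection leaves open is an objective count. The 7.2 reporting instruction is qualified by the subject's baseline and circumstances, and 7.1.4 exempts some laboratory abnormalities from discontinuation at the investigator's judgement. The AESI and discontinuation tables therefore count what was reported. A listing contains the values but gives no count by arm.

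**Conclusion.** The point holds as a gap in safety reporting. No planned summary gives, by treatment, the number of subjects whose laboratory data crossed the hepatic or creatinine-clearance thresholds of 7.2, and the omission is not declared. It would be too strong to say that CTCAE grading fails across the board, or only when baseline is abnormal. It recovers the 3x and 5x ULN cuts from a normal ALT or AST baseline and blurs them from an abnormal one. It does not isolate the 8x, bilirubin or joint criteria at either kind of baseline, and it misses a halved clearance at low-normal creatinine.

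The number of subjects affected cannot be estimated, because the documents give no distribution of baseline ALT, AST or creatinine. The conclusion assumes that 8.8.4 refers to 7.2, and that age and ideal body weight are constant over the treatment period. It does not depend on an assumed laboratory normal range, since everything is expressed in multiples of ULN.

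For the Maintenance SAP the point is weaker. Its Section 1 announces an abbreviated report after early termination, without every protocol-defined analysis.

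**What to change.** In Phase 2b SAP 3.7.3.1, add number-and-percentage rows by treatment at the protocol's existing thresholds:
- AST or ALT above 3x, above 5x and above 8x ULN;
- AST or ALT above 3x ULN with bilirubin above 2x ULN;
- creatinine clearance down by at least 50% from Day 1.

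Show any occurrence separately from the repeat-report version wherever 7.2 requires two reports. State that both use all post-baseline results, including repeats: SAP 3.1.4 keeps only the latest laboratory result in a visit window, which could replace the first high value with its recheck. The INR and symptom arms can stay with AESI reporting, since INR is measured locally.

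In the Maintenance SAP, add the same rows or state in Appendix 5.1 that they are omitted. In Protocol 8.8.4, change the cross-reference to Section 7.2.

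The cost is a few table rows from data already collected. No new clinical threshold is proposed.
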